### **Appearance of donor-specific anti-HLA antibodies (DSA) and acute rejection.**

Steroid withdrawal at the third month post-transplant did not result in the appearance of DSA in patients with a low immunological risk, at least during the first two years of follow-up and using a MFI >500. No significant differences were found in the number of patients who experienced acute rejection after randomization between Group A (7.14%) and Group B (11.54%).

### **Histological study of the protocol biopsies**

The results of the protocol biopsies showed that the patients who had subclinical inflammation of the graft at the third month post-transplant had more chronic lesions (p=0.008) and worse renal function than the patients who had no inflammatory lesions. Likewise, the patients who had subclinical tubulo-interstitial inflammation (borderline lesions) 24 months post-transplant had more chronic lesions than those who had no subclinical inflammation (p=0.023) and this was more relevant in those patients who continued to receive prednisone (p=0.020).

The patients with and without subclinical tubulo-interstitial inflammation at the third month post-transplant experienced a significant increase in inflammation (t, i) ( $p<0.001$  and  $p=0.058$ ) and chronic parameters (ct, ci) ( $p=0.017$  and  $p=0.017$ ) at 24 months post-transplant.

Finally, at 24 months post-transplant the increase in acute and chronic lesions ( $p=0.019$  and  $p=0.009$ ) was more relevant in those patients who had borderline lesions at the third month and who ceased steroids.

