### *Secondary objectives*

1. To determine the course of the histological findings in the two treatment groups.
2. To determine the course of the balance in the subpopulations of lymphocytes (CXCR3highCD4+/CCR4highCD4+) and regulatory cells (Treg CCR4high) using flow cytometry in samples from peripheral blood and FNAP after withdrawal of steroids in the third month post-transplant versus conventional triple immunosuppression.
3. To analyze and compare the incidence of immunological dysfunction in the two treatment arms, as well as graft and patient survival at one and two years of follow-up.
4. To examine the potential metabolic and cardiovascular benefit of steroid withdrawal in terms of renal function, hypertension, diabetes and hyperlipidemia.
5. To assess the adherence to treatment with immunosuppressors in the two treatment groups and its impact on the generation of DSA.

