### **Variables:**

#### *Efficacy variables:*

The *primary variable* was the presence of donor-specific anti-HLA antibodies (DSA) at 24 months.

The *secondary variables* were:

- a) Graft and patient survival.
- b) Rate of acute clinical rejection, confirmed by biopsy, calculated glomerular filtration rate (determined by aMDRD) and proteinuria at 3, 6, 12 and 24 months.
- c) BP figures and number of hypertensive patients, lipid levels and need for lipid-lowering drugs, and increase in weight and BMI.
- d) Rate of post-transplant diabetes mellitus (PTDM) or glucose intolerance one year post-transplant according to the criteria of the ADA (PTDM: baseline glycemia  $\geq 126$ , or  $\geq 200$  mg/dl after glucose overload, or need for treatment; glucose intolerance: glycemia after overload of 140-199 mg/dL).
- e) Determination of the lymphocyte subpopulations (CXCR3highCD4+; CCR4highCD4+ and Treg CCR4high) by flow cytometry at 1, 3, 6, 12, 18 and 24 months.
- f) Appearance of acute or chronic pathological lesions of the graft using:

\*Kidney graft biopsy. Biopsies were done before randomization (month 3 post-transplant) and in month 24 post-randomization (protocol biopsies). In the case of suspected acute rejection a biopsy of the graft was done before or within 48 hours of starting anti-rejection treatment. Likewise, a graft biopsy was done at any time if graft dysfunction was detected, as evidenced by proteinuria 0.5 g/day or an increase in the serum creatinine of 25% above its baseline level. The biopsies were evaluated according to the Banff'09 classification (*Sis B, et al Am J Transplant 2010;10: 464-71*). Biopsies done for clinical indication and those done prior to randomization were evaluated locally at each participating center. The local pathologist interpreted the biopsy for the presence of clinical or subclinical rejection, borderline lesions or progression of chronic lesions that

explained a possible graft failure to thus provide the most opportune treatment. The biopsies done and the pre-randomization and final visits were also sent to the pathologist at Carlos Haya Hospital, Malaga, who also interpreted and classified them using the same Banff'09 criteria. The biopsies were processed in each center and sent to the central pathologist for study. The slides comprised at least 2-3 slices of the biopsy. The staining was done locally (hematoxylin eosin, periodic acid Schiff, Masson trichrome and methenamine silver).

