For the measurement of C4d an unstained slide was sent to the reference center, at ambient temperature.

\*The interpretation of the central pathologist was used mainly to analyze the progression of the chronic graft nephropathy. For each patient, the sum of the classification of the chronic lesion was obtained from the 5 histological categories: 1) cg: chronic glomerulopathy. 2) ci: chronic interstitial. 3) ct: tubular atrophy (chronic). 4) cv: arteriolar hyalinosis (chronic). 5) mm: mesangial matrix.

*Confounding variables:* Donor and recipient age, HLA compatibility and PRA, delayed graft function, BMI, CMV infection, concomitant treatment (statins, ACEIs/ARA, beta blockers, diuretics, and ASA), scale of treatment compliance and levels of tacrolimus or CsA.

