## **STATISTICAL ANALYSIS PLAN.**

Descriptive statistics are presented together with the various analyses. Both an intention-to-treat analysis and an analysis according to the final treatment were done. The categorical variables were analyzed using the chi-square test or Fisher's exact test, according to needs. The quantitative data were analyzed using the Student t test or the Mann-Whitney U test, according to needs. Changes over time in the DSA and lymphocyte subsets in the two study groups were analyzed using a general linear model for repeated measures, adjusting for confounding variables. Correlations between the various subsets were analyzed using Pearson correlation. The graft and patient survival curves were calculated with the Kaplan-Meier method. The rates of survival of the groups were compared with the log-rank test. Finally, a linear regression analysis was done to determine the factors associated with the generation of de novo DSA, including steroid withdrawal. The data were analyzed using SPSS 20.0.

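### Secondary objective 1 asks for histology by treatment group, but no overall Group A versus Group B histology contrast is specified or reported, and the arm-specific statements name no test

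*Combined protocol and SAP*

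**What the plan says.** Item 1 of the Secondary objectives is: "To determine the course of the histological findings in the two treatment groups". The Efficacy variables section lists as a secondary variable "Appearance of acute or chronic pathological lesions of the graft using" protocol biopsies before randomisation (month 3) and at the end of follow-up. It adds a central reading and a summary score: "For each patient, the sum of the classification of the chronic lesion was obtained from the 5 histological categories".

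The Statistical Analysis Plan does not mention histology by name. Its longitudinal between-group model is assigned elsewhere: "Changes over time in the DSA and lymphocyte subsets in the two study groups were analyzed using a general linear model for repeated measures". Histology is left to general rules by data type: "The categorical variables were analyzed using the chi-square test or Fisher's exact test, according to needs" and "The quantitative data were analyzed using the Student t test or the Mann-Whitney U test, according to needs". No alpha, hierarchy, multiplicity rule or exploratory label is given.

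The results under Histological study of the protocol biopsies contain nine p-values. They include the comparison that "the patients who had subclinical inflammation of the graft at the third month post-transplant had more chronic lesions" and the statement that the increase in acute and chronic lesions "was more relevant in those patients who had borderline lesions at the third month and who ceased steroids".

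**The concern.** Only a comparison of Group A with Group B is protected by randomisation, and that is the comparison the objective points to. The plan supplies a suitable score and two biopsy time points but never joins them to a between-arm test, and the results give no overall arm difference, confidence interval or number of biopsies per arm. The sections on rejection, diabetes, lipids, blood pressure, renal function and safety all give figures by arm.

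What fills the space are associations and two arm-specific statements that point in different directions. The link between month-24 borderline inflammation and chronic lesions is said to matter more in patients who stayed on prednisone. The increase in lesions is said to matter more in month-3 borderline patients who stopped steroids. Without an overall arm result, or a test that the arms differ in these respects, a reader may take either one as an effect of continuing or withdrawing steroids.

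**Working it through.** **1. Sorting the nine p-values by the question each answers** (all from Histological study of the protocol biopsies)

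| p-value | Comparison as described | Arm contrast? |
|---|---|---|
| 0.008 | month-3 inflammation vs none, chronic lesions | no |
| 0.023 | month-24 borderline vs none, chronic lesions | no |
| <0.001, 0.058 | increase in inflammation scores (t, i) to month 24 | no |
| 0.017, 0.017 | increase in chronic scores (ct, ci) to month 24 | no |
| 0.020 | month-24 association, prednisone continued | not stated |
| 0.019, 0.009 | increase in acute and chronic lesions, month-3 borderline and steroids stopped | not stated |

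That is six values unrelated to arm and three related to arm by an unstated test. For the three, the text also does not say whether patients are grouped as randomised or by final treatment, although the Statistical Analysis Plan provides for both. The paired values for t and i could refer to the two scores or to patients with and without inflammation. The 0.058 sits in a sentence that calls the increase significant.

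**2. What the arm-related statements condition on.** The 0.020 statement splits patients by inflammation at month 24. That is a post-randomisation outcome which steroid withdrawal could itself change, so the split is not protected by randomisation. The 0.019 and 0.009 statement splits by month-3 status, which precedes randomisation. It could support a valid subgroup contrast, but only with an arm-by-borderline interaction test.

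**3. Are the p-values unadjusted?** The histology section gives no n, mean or SD, so its p-values cannot be re-derived. The safety section can be checked. With 52 and 53 patients its percentages correspond to 5 vs 12, 3 vs 2 and 2 vs 1 events. Fisher's exact test gives 0.110, 0.678 and 0.618, against 0.110, 0.677 and 0.618 printed. Those are nominal values. That the histology values are nominal too is an inference, since no correction is mentioned.

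**4. How much does a correction change?** Assumptions, neither from the documents: alpha 0.05, and the printed values as the family. Take <0.001 as 0.001 and sort: 0.001, 0.008, 0.009, 0.017, 0.017, 0.019, 0.020, 0.023, 0.058.

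- Holm, m=9 (running maximum of (m−j+1)·p): 9×0.001=0.009; 8×0.008=0.064; 7×0.009=0.063, raised to 0.064; 6×0.017=0.102; the rest stay at 0.102. **One** is below 0.05.
- Hochberg, m=9 (start from the largest): 0.058>0.05; 0.023≤0.05/2=0.025, so all from 0.023 down are rejected. **Eight** are kept. Hommel also keeps eight.
- Benjamini-Hochberg: 0.023≤8×0.05/9=0.044. **Eight** are kept.
- Holm on the three arm-related values: 3×0.009=0.027; 2×0.019=0.038; 0.020, raised to 0.038. **Three of three** are kept.

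Nine is a minimum, because the section also claims worse renal function in inflamed patients without a p-value. With one extra test at an illustrative p=0.20 (m=10), Hochberg compares 0.058 with 0.025, 0.023 with 0.0167, 0.020 with 0.0125, and so on, and keeps only the smallest value. If the extra p were 0.01 or 0.024, it would still keep eight. The count therefore turns on comparisons that the document does not enumerate.

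**The case against.** The plan is not empty on histology. The objective names both groups, biopsy times and a central Banff reading are fixed, the chronic sum is defined, and the Statistical Analysis Plan has generic two-group tests and an intention-to-treat analysis. The results are headed as preliminary, and an unprinted arm comparison may still have been run. Formal multiplicity control across secondary histology outcomes in a phase IV trial is a matter of judgement. All of this stands: the contrast is under-specified rather than excluded, and the gap is that it is neither tied to the score nor reported.

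A reader might go further and infer that only one histology finding survives correction, so the rest fail. The documents do not support that. The single survivor comes from applying Holm to a pooled family of nine that mixes associations, time trends and arm-related statements. Other recognised procedures keep eight of the same nine, and the arm-related values taken alone all pass Holm. Hochberg and Hommel need independence or suitable positive dependence to control family-wise error, which is plausible for related lesion scores but cannot be verified here.

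A reader might also quote an inflated false-positive rate. For nine independent true nulls at 0.05 it is 1−0.95^9=0.370, but it falls towards 0.05 as the correlation approaches 1. The documents give no correlation, so no minimum inflation can be claimed.

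**Conclusion.** The point holds for specification and reporting. The plan links no between-arm analysis to the central chronic sum, and no overall Group A versus Group B histology result is printed. Six of nine p-values do not address the randomised question. The other three do not reveal what was tested, and one of them conditions on a post-randomisation outcome. With no multiplicity rule, all nine are hypothesis-generating.

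No count of survivors should be used as a measure of the problem: it ranges from one to eight of nine with the procedure, at an assumed alpha of 0.05 and an assumed family. Nor do the documents show that the arm-specific findings are false, or that steroid withdrawal has or lacks a histological effect. They do not report the comparison that would tell. The matter concerns a secondary objective, leaves the primary DSA comparison untouched, and is worth correcting because the readings already exist.

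**What to change.** - **Between-arm contrast.** In the Statistical Analysis Plan, and first in the histology results, give the Group A versus Group B difference in the central five-category chronic sum at the final protocol biopsy. Include all randomised patients with a biopsy, analysed as randomised and adjusted for the month-3 value. Report the estimate, 95% CI and n per arm. State the time origin of the final biopsy: the Efficacy variables section counts month 24 from randomisation, the results from transplant.
- **Arm-specific statements.** Support each with an arm-by-inflammation interaction test, or describe it as within-arm only. Where the inflammation is measured at month 24, present it as an association even if the interaction is shown.
- **Labels.** Results are already known, so mark the between-arm contrast and the interactions as post hoc. Mark every other histology comparison as exploratory, and state how many comparisons were made. Formal adjustment of the exploratory values is optional; if it is used, state the procedure and family.

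The cost is a little more analysis of readings already collected, plus wording changes. The downside is that the present histology statements become exploratory.

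### No confounder adjustment is specified or reported for the non-randomised inflamed versus non-inflamed biopsy contrasts, and the planned chronic lesion sum is not compared overall between arms

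*Combined protocol and SAP*

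**What the plan says.** The first item under Secondary objectives is the course of the histological findings in the two treatment groups. Under Efficacy variables, the central pathologist's reading serves mainly to follow progression of chronic graft damage, and the score is defined: "For each patient, the sum of the classification of the chronic lesion was obtained from the 5 histological categories". The same section lists confounding variables, beginning "Donor and recipient age, HLA compatibility and PRA, delayed graft function".

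The Statistical Analysis Plan uses confounders in one stated place. Changes over time in DSA and lymphocyte subsets "in the two study groups were analyzed using a general linear model for repeated measures, adjusting for confounding variables". The only other multivariable model is a linear regression for factors associated with de novo DSA. For other quantitative data the rule is general: "The quantitative data were analyzed using the Student t test or the Mann-Whitney U test, according to needs". Categorical data go to chi-square or Fisher tests.

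The histology results then open with "patients who had subclinical inflammation of the graft at the third month post-transplant had more chronic lesions (p=0.008) and worse renal function". For renal function no p value is given. Next, patients with borderline lesions at "24 months post-transplant had more chronic lesions than those who had no subclinical inflammation (p=0.023"). Later sentences report increases in inflammation and chronic scores up to month 24, and a final result that "was more relevant in those patients who had borderline lesions at the third month and who ceased steroids".

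**The concern.** Inflammation status is observed, not assigned. Donor age and delayed graft function, both on the protocol's own list, could plausibly raise both early inflammation and chronic lesion scores. If they do, an unadjusted comparison attributes their effect to inflammation. The month-3 contrast is also reported as a level of lesions, with no mention of the chronic score already present at month 3.

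Two things are at stake. One is how far the associations at p=0.008 and p=0.023 can be read as more than markers of graft quality. The other is the first secondary objective: without an overall arm comparison of the chronic sum, the reader has only subgroup statements about steroids (p=0.020 in those continuing prednisone; p=0.019 and p=0.009 in month-3 borderline patients who stopped) and no overall effect to set them against. The primary DSA result is not affected.

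**Working it through.** **1. Reproducing the reported figure.** This cannot be done. The results give p=0.008 without group sizes, means, SDs, the test used or the time point of the chronic lesions. What follows is a sensitivity calculation, treating the p value as two-sided from a two-sample t test.

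**2. Plausible n.** The upper value is 105 (52 + 53), if only randomised patients were analysed. A lower guide comes from the section on lymphocyte subpopulations, which correlates a month-3 subset with month-24 inflammation. With t = r√(n−2)/√(1−r²):
- r = 0.431, n = 38: t = 0.431 × 6/0.902 = 2.87, p = 0.007
- r = 0.436, n = 37: t = 0.436 × 5.916/0.900 = 2.87, p = 0.007

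Both match the reported P=0.007. These are patients with cytometry as well as biopsy, so 38 is a guide and not the n of the biopsy contrast.

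**3. Difference implied by p=0.008.** d = t × √(1/n₁ + 1/n₂). Assumption: 30% inflamed.
- n = 38 (11.4 and 26.6): 2.81 × 0.354 = 0.99 SD
- n = 105 (31.5 and 73.5): 2.70 × 0.213 = 0.58 SD

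With 20% or 40% inflamed, d is 1.14 or 0.93 at n = 38, and 0.66 or 0.54 at n = 105.

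**4. Illustrative confounding by donor age.** Assumptions, none from the documents: a donor-age gap between groups of 0.3 to 0.7 SD, and a correlation of donor age with the chronic score of 0.3 to 0.5. Spurious difference ≈ gap × correlation, from 0.3 × 0.3 = 0.09 SD to 0.7 × 0.5 = 0.35 SD.

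| n | Implied difference | Spurious share |
|---|---|---|
| 38 | 0.99 SD | 9% to 35% |
| 105 | 0.58 SD | 16% to 61% |

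**5. Effect on the p value.** Partial r = (r_xy − r_xu·r_yu)/√((1−r_xu²)(1−r_yu²)), where x is inflammation, y the chronic score and u donor age. A 0.7 SD gap with 30% inflamed gives r_xu = 0.7√0.21/√(1 + 0.49 × 0.21) = 0.305. With r_yu = 0.5:
- n = 38: r_xy = 0.424, partial r = 0.329, p = 0.047
- n = 105: r_xy = 0.258, partial r = 0.127, p = 0.20

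Over the whole assumed range, adjusted p runs from 0.011 to 0.047 at n = 38 and from 0.019 to 0.20 at n = 105.

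**6. Confounding needed to change the reading.** Let one confounder have the same correlation c with inflammation and with the chronic score. Then p passes 0.05 at c of about 0.38 (n = 38) or 0.28 (n = 105). The association vanishes at c of about 0.65 or 0.51. In 20,000 simulated trials with no true inflammation effect and c = 0.3, the unadjusted 5% test rejected in 8% (n = 38) and 15% (n = 105); the adjusted test stayed at about 5%.

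**The case against.** The other side has several good points.

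- A reader might infer that adjustment was granted to the randomised histology comparison and withheld from the non-randomised one. The plan does not say that. Its adjusted model covers DSA and lymphocyte subsets only, so histology has no adjusted model of either kind. Adjusting a randomised comparison is in any case legitimate.
- A reader might infer that unadjusted tests were run. The results name no test. What stands is that no adjustment is specified or reported.
- A reader might infer that progression was ignored. It was not: later sentences report increases to month 24. The point about the month-3 score concerns only the leading contrasts, and for p=0.008 even the time point of the lesions is unstated.
- The wording is already associational, the section is headed preliminary, and no imbalance in donor age or delayed graft function is shown. The exclusions for creatinine above 2 mg/dL, proteinuria above 1 g/day and cold ischaemia above 30 hours narrow graft quality among randomised patients.
- The confounding inputs are assumed. At n = 38 even the largest of them leaves p just under 0.05. The c = 0.4 case, which would take p to 0.058 there, needs a donor-age gap of about 0.95 SD, beyond the assumed range.
- A model with many covariates would be overfitted at n near 38, and the month-3 chronic score may lie on the pathway from inflammation.

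These points limit the strength of the claim and the size of the model. They do not supply an adjusted analysis or the overall comparison by arm.

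**Conclusion.** The point holds as a gap in specification and reporting. The inflamed versus non-inflamed contrasts are non-randomised, and no adjustment is planned or reported for them although relevant confounders are listed. The associations at p=0.008 and p=0.023 may partly reflect donor or early-graft quality. The documents do not show that they do, so it would go too far to call them artefacts.

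The magnitude is illustrative: 9% to 35% of the month-3 difference at n = 38, or 16% to 61% at n = 105, given 30% inflamed and the assumed donor-age inputs. The two ranges should not be merged, because each belongs to its own sample size.

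The month-24 contrast has a further limit. Inflammation and chronic lesions are measured together and after randomisation, so covariates alone could not establish direction. The final result, in month-3 borderline patients who stopped steroids, involves the randomised factor within a subgroup; its difficulty is subgroup and interaction reporting more than donor confounding.

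Separately, no overall Group A versus Group B comparison of the five-category sum is reported, so the first secondary objective lacks its planned result.

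**What to change.** 1. Make the primary histology result the month-24 centrally read chronic sum by arm, adjusted for the month-3 sum, in a linear or ordinal model.
2. Then estimate the association of month-3 inflammation with the month-24 sum in a regression with arm and two or three listed confounders: donor age, delayed graft function, and HLA compatibility if n allows. Fit it with and without the month-3 chronic sum, since that score may be on the pathway.
3. For each result give n per group, time point, difference and confidence interval. State who forms the month-3 inflamed group, because subclinical rejection in that biopsy was an exclusion and accounted for 20.3% of screening failures.
4. Label the month-24 inflammation contrast (p=0.023) as a concurrent, unadjusted, exploratory association.

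The cost is analysis time only, since the covariates are already on the protocol's list. The downside is wider intervals and, if n is near 38, room for only a few covariates. If even that is not workable, label the month-3 contrast as unadjusted and exploratory too.

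### Two histology effects are reported as more relevant in one arm, but no between-arm or interaction result is given to show it, and one of them is split by a finding made after randomisation

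*Combined protocol and SAP*

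**What the plan says.** The histology results stand under Preliminary results, in Histological study of the protocol biopsies. Two statements there are specific to an arm.

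- **Claim 1.** Overall, "the patients who had subclinical tubulo-interstitial inflammation (borderline lesions) 24 months post-transplant had more chronic lesions" "than those who had no subclinical inflammation (p=0.023"; the sentence then adds that "this was more relevant in those patients who continued to receive prednisone (p=0.020".
- **Claim 2.** The increase in acute and chronic lesions at 24 months (p=0.019 and p=0.009) "was more relevant in those patients who had borderline lesions at the third month and who ceased steroids".

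On timing, Efficacy variables states: "Biopsies were done before randomization (month 3 post-transplant) and in month 24 post-randomization (protocol biopsies". The results date the final biopsy from transplant instead, but on either dating it follows randomisation.

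The Statistical Analysis Plan gives these methods for general use: "The categorical variables were analyzed using the chi-square test or Fisher's exact test, according to needs" and "The quantitative data were analyzed using the Student t test or the Mann-Whitney U test, according to needs". Its only model for change by arm is limited to other outcomes: "Changes over time in the DSA and lymphocyte subsets in the two study groups were analyzed using a general linear model for repeated measures". The rest is Pearson correlation between subsets, Kaplan-Meier and log-rank for survival, and a linear regression for de novo DSA. The histology entry under Secondary objectives concerns the course in each treatment group and names no subgroup.

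**The concern.** To say that an effect is more relevant in one arm is to say that it differs between arms. That needs an estimate of the difference with its uncertainty. A small p-value in one arm does not supply it, because the other arm may show a similar effect with a larger p-value.

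Claim 1 has a second problem. Borderline status at 24 months can itself be affected by whether steroids were continued. Patients with 24-month borderline lesions in one arm are therefore not the randomised counterparts of those in the other, and a contrast between arms within that split is no longer protected by randomisation.

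These are the only arm-specific statements in the histology section. A reader could carry them away as evidence of how steroid withdrawal acts on the graft in particular patients.

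**Working it through.** **What can be reproduced.** Nothing directly. The section gives no counts, means, standard deviations or test names, so p=0.020, 0.019 and 0.009 can be neither reproduced nor refuted. What can be checked is what they would imply.

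**Claim 1, implied interaction.** Inputs: overall p=0.023 and prednisone-arm p=0.020, both from the histology section. Assumptions: the first is the pooled test; the second is a test within the prednisone arm; the pooled result is the information-weighted combination of the two arms. Let f be the prednisone arm's share of the information. The documents do not give f; 0.5 is a natural centre, since 52 and 53 patients were randomised.

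- z_pooled = 2.273 and z_A = 2.326 (two-sided).
- z_B = (z_pooled − √f·z_A) / √(1−f)
- z_int = √(1−f)·z_A − √f·z_B

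At f = 0.5: z_B = (2.273 − 0.707×2.326)/0.707 = 0.89, and z_int = 0.707×(2.326 − 0.89) = 1.02, so p = 0.31.

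| f | Withdrawal arm z (p) | Interaction z (p) |
|---|---|---|
| 0.3 | 1.19 (0.23) | 1.29 (0.20) |
| 0.5 | 0.89 (0.37) | 1.02 (0.31) |
| 0.7 | 0.60 (0.55) | 0.78 (0.44) |

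On this reading the withdrawal arm shows an association in the same direction, and the difference between arms is not significant anywhere in the range.

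**Claim 2, two readings.** No pooled or other-arm p-value is given, so no interaction p can be derived.

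- *Tests within the withdrawal arm.* For a between-arm contrast to reach 0.05 at equal information, the other arm needs z ≤ z_obs − 1.96·√2. That is 2.345 − 2.772 = −0.43 for p=0.019, and 2.612 − 2.772 = −0.16 for p=0.009: an effect in the opposite direction. If the withdrawal arm held 30% of the information, the limits would be 0.00 and 0.41; at 70%, −0.81 and −0.63. The section does not report what the other arm showed.
- *Tests between arms among month-3 borderline patients.* The planned two-group tests cover this, and it would support a difference between arms within that subgroup. It would not show that the difference is larger than in patients without borderline lesions.

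**Multiplicity.** The section reports nine p-values with no adjustment. A Bonferroni threshold would be 0.05/9 = 0.0056, which 0.020, 0.019 and 0.009 all miss.

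**Power for an interaction.** An interaction as large as a main effect detectable with 80% power has expected z = (1.96 + 0.84)/2 = 1.40, hence power Φ(1.40 − 1.96) = 29%. The numbers are probably small. Under Lymphocyte subpopulations, r = −0.431 and r = −0.436, each with P=0.007, imply about 38 and 37 patients through t = r·√((n−2)/(1−r²)), if these are plain Pearson tests. That counts patients with both the 3-month subset and 24-month histology, so the number of 24-month biopsies could be higher.

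**The case against.** The strongest reply is that the absence of an interaction test is inferred. The section names no test, so an unreported interaction or between-arm comparison cannot be excluded. This stands, and it limits the point to what is shown as reported. A reader might go further and infer that the claims are false, or that the arms have been shown not to differ. The documents do not support that: the interaction p of 0.31 depends on an assumed reading and an assumed information split, and a non-significant interaction at this size would not establish equal effects.

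Second, claim 2 should not be judged like claim 1. Its subgroup is fixed before randomisation, and its wording fits a plain comparison of change between arms among borderline patients, which the plan's two-group tests allow. This also stands. The subgroup is sound; what is missing is the contrast tested and any comparison with non-borderline patients.

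Third, a reader might infer that the two claims contradict each other because they single out opposite arms. They do not. Claim 1 relates two findings in the same 24-month biopsy; claim 2 concerns an increase by 24 months in patients grouped at month 3. Both could be true.

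Fourth, the results are labelled preliminary, serve a secondary objective and make no recommendation on who may stop steroids. That is correct and limits the consequence. It does not supply the missing comparison, since the sentences are worded as findings. Nor does it help claim 1 that it describes an association: the association stands as description, but the contrast between arms attached to it does not.

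**Conclusion.** The point holds in limited form. As reported, neither arm-specific statement is shown, because the other arm's result, estimates, counts, tests and interaction results are all absent and no arm-by-subgroup analysis of histology was planned.

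For claim 1 the difficulty would remain even if p=0.020 were an interaction p-value, because the split is made on a post-randomisation finding. On the natural reading, the section's own two p-values give no evidence that the arms differ. For claim 2 the conclusion depends on which test was run: unsupported if within-arm, and incomplete as a statement about borderline status if between arms.

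Timing, the list of planned methods and the missing items are read directly from the documents. The size of the implied interaction is illustrative. The matter deserves correction because it changes what can be concluded from the histology, on a secondary outcome and at little cost.

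**What to change.** 1. For each arm-specific statement, give the test used, the number of patients and the estimate with 95% CI in each arm, and say whether patients were grouped by randomised arm or by final treatment.
2. For the sum of chronic scores and for i, t, ci and ct, fit one model each with arm, month-3 borderline status, their interaction and the month-3 score. Report the interaction estimate with its 95% CI and p-value.
3. Label these models post hoc and exploratory, so that they are not taken as pre-specified. State how many outcomes were tested. Note that power for the interaction is low and that a non-significant result does not show equal effects.
4. Present the 24-month inflammation result as a descriptive association pooled over arms, without an arm contrast.
5. Remove the wording *more relevant* wherever no between-arm or interaction estimate supports it.

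The cost is a re-run on data already held and a revision of the histology text. The downside for the sponsor is that the arm-specific claims may not survive.
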